### **5.9.4 Safety Analysis**

All subjects who have been allocated to the DING intervention will be included in the safety analysis. The frequencies of AEs will be summarized. SAEs (if any) will be described in detail.

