#### 3.1.1 Screening Phase

Potential subjects will be screened on an antenatal basis in the CHOP Center for Fetal Diagnosis and Treatment (CFDT) and the SDU. We will identify and screen all women carrying a fetus at least 32 weeks gestation with a prenatal diagnosis of

---

CDH who plan to deliver in the CHP SDU. We will approach the parents during a prenatal visit at the CFDT or on an antenatal inpatient basis in the SDU to offer study participation and obtain informed consent. Given that the subjects are neonates, we will not obtain assent.

For fetuses with parental consent, we will then review the eligibility criteria again prior to and during delivery. Subjects with signed antenatal informed consent who meet all eligibility criteria will be allocated to the trial intervention at the time of birth.

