### **3.4.2 Exclusion Criteria**

1. Multiple gestation
2. Major anomalies or aneuploidy
3. Enrolled in FETO (fetal endoluminal tracheal occlusion) trial
4. Palliative care planned or considered
5. Maternal diagnosis placenta previa, accreta, or abruption
6. Maternal diagnosis pre-eclampsia requiring Magnesium sulfate therapy at time of delivery
7. OB or Neonatal provider concerns for the clinical care of the mother or infant, or study team not available.

The inclusion and exclusion criteria are the same for the interventional arm and the historical controls. Subjects that do not meet all of the enrollment criteria may not be enrolled. Any violations of these criteria must be reported in accordance with IRB Policies and Procedures.

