### 5.11 Interim Analysis

An independent data and safety monitoring board (DSMB), comprising a clinical epidemiologist and two clinical content experts, will review specified safety events incrementally after allocation of every 5 subjects to ensure the study does not impose undue extra risk on infants with CDH.

As this is a single-arm trial, there are no early stopping rules for efficacy.

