## 6 STUDY INTERVENTION

### 6.1 Description

All eligible infants will be allocated to receive the DING intervention. Immediately after birth, the infant will be placed on a LifeStart trolley with an intact umbilical cord, intubated, and ventilated according to the CHOP clinical “Gentle ventilation” protocol. UCC will occur after (1) colorimetric end-tidal CO2

Figure 1: DING intervention during vaginal delivery, using LifeStart Trolley

detection or (2) 3 minutes after delivery, whichever occurs first. DCC has been variably defined in studies, using a time-based approach (ranging from 1-5 minutes) or physiologic approach (ie: cessation of cord pulsation, or placental descent). An upper limit of 3-minutes prior to UCC was selected through discussion with the clinical team, as this interval would allow sufficient time for the neonatal team to establish lung aeration prior to placental separation, while also avoiding a delay in transferring the infant to the infant stabilization suite. A retrospective review of intubations performed at CHOP demonstrated a 62% first-attempt success rate for attending neonatologists, and over 85% of attending neonatologists were successful within the first 2 intubation attempts. Thus, we anticipate that 3 minutes is a sufficient time period for most DING trial participants to be successfully intubated prior to UCC.

The Lifestart trolley is a small resuscitation trolley specifically designed to facilitate neonatal resuscitation with an intact umbilical cord. The trolley includes a warmer mattress and has FDA 510K clearance (See attachment). The CHOP Medical Device Committee approved the Lifestart trolley for use in this DING trial. The trolley will be positioned next to the mother covered in a sterile drape prior to the delivery. The senior neonatal clinician (who will perform the intubation and is a member of the study team), the neonatal nurse, and the neonatal respiratory therapist will all attend the infant during the DING intervention.

Immediate cord clamping will be performed for any of the following:

- Inadequate umbilical cord length or inability to adequately position infant on the trolley for intubation
- If the neonatologist or obstetrician has any concerns about the infant or mother's safety or the team's ability to perform clinical interventions

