## **8.4 Regulatory and Ethical Considerations**

### **8.4.1 Data and Safety Monitoring Plan**

After each DING intervention is attempted, the Principal Investigator will review medical record and video recordings and debrief the clinical staff to ascertain potential safety and feasibility concerns. The Principal Investigator will provide oversight for emerging safety information.

In addition, a Data Safety Monitoring Board (DSMB), comprising two clinical content experts and a neonatal clinical trialist, will review specified safety events incrementally after allocation of every 5 subjects to ensure the study does not impose undue extra risk on infants with CDH.

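### Safety is tabulated only on all allocated subjects, so if some infants are clamped before any intact-cord attempt, rates of procedure-specific harm can be understated

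*Combined protocol and SAP*

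**What the plan says.** Section 5.9.4 (Safety Analysis) defines the safety set in one sentence: "All subjects who have been allocated to the DING intervention will be included in the safety analysis". It promises AE frequencies and a description of each SAE. No set based on exposure or attempt is defined.

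Section 3.1.1 fixes the moment of allocation: "Subjects with signed antenatal informed consent who meet all eligibility criteria will be allocated to the trial intervention at the time of birth". Section 6.1 then lists what can follow: "Immediate cord clamping will be performed for any of the following". The first trigger is "Inadequate umbilical cord length or inability to adequately position infant on the trolley for intubation". The second is "If the neonatologist or obstetrician has any concerns about the infant or mother's safety or the team's ability to perform clinical interventions".

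Sections 5.11 and 8.4.1 say that the DSMB "will review specified safety events incrementally after allocation of every 5 subjects". On stopping, 5.11 says only "As this is a single-arm trial, there are no early stopping rules for efficacy"; no numeric safety threshold appears anywhere.

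Other sections use a different unit. Section 7.3 defines an adverse event in someone who has actually received an intervention, and 8.4.1 has the principal investigator review each case once the procedure has been attempted. Section 5.3 records whether the infant was successfully positioned, whether intubation preceded clamping (and if not, why), the number of attempts and the time from birth to clamping. Section 5.2.2 adds a camera mounted on the trolley.

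**The concern.** Safety is half of the primary objective in section 2.1, and section 5.10 says the trial is meant to supply estimates for later randomised trials. Section 8.4.2 attributes avulsion, cooling and contamination of the surgical field to the trolley procedure. There is no concurrent comparator, so the safety result is simply a count over a denominator.

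Intention to treat suits the feasibility endpoint, where an infant clamped at once is a failure and should count as one. As the only denominator for harms of the procedure, it can include infants in whom the procedure was never tried. Any resulting error in the rate is towards reassurance, and it grows with the number of such infants. The same wording means that a DSMB review described as covering five subjects does not tell the board how many of them underwent an attempt.

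**Working it through.** **Inputs.** Allocated subjects: 20 (section 3.3.2). DSMB block: 5 allocations (5.11, 8.4.1). Number of allocated infants clamped before any intact-cord attempt, k: not given, so taken as 0 to 5 as an assumption. The plan states no safety rate, limit or threshold, so there is no figure of its own to reproduce.

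**Step 1: can an allocated infant be unexposed?** Yes. Allocation is at birth (3.1.1, 3.1.2) and the immediate-clamping triggers in 6.1 apply afterwards. The route is narrower than it first looks, for two reasons. A concern recognised before allocation makes the dyad ineligible under exclusion 7 ("OB or Neonatal provider concerns for the clinical care of the mother or infant, or study team not available"). And an infant who could not be positioned has usually been through an attempt.

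**Step 2: direction.** Let p1 be the event risk with an attempt and p0 the risk without one. The expected all-allocated rate is [(20 − k)·p1 + k·p0]/20, which falls short of p1 by k·(p1 − p0)/20. If the event cannot occur without the procedure (p0 = 0), the rate is multiplied by (20 − k)/20. Avulsion from trolley positioning is close to that case. Hypothermia on the first temperature has other causes, so p0 > 0 and the shortfall is smaller.

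**Step 3: size.** With zero events in n = 20 − k, the exact two-sided 95% upper limit is 1 − 0.025^(1/n).

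| k (assumed) | n | Factor if p0 = 0 | Zero-event upper limit | One event: /20 → /n | Two events: /20 → /n |
|---|---|---|---|---|---|
| 0 | 20 | 1.00 | 16.8% | 5.0% → 5.0% | 10.0% → 10.0% |
| 1 | 19 | 0.95 | 17.6% | 5.0% → 5.3% | 10.0% → 10.5% |
| 2 | 18 | 0.90 | 18.5% | 5.0% → 5.6% | 10.0% → 11.1% |
| 3 | 17 | 0.85 | 19.5% | 5.0% → 5.9% | 10.0% → 11.8% |
| 4 | 16 | 0.80 | 20.6% | 5.0% → 6.3% | 10.0% → 12.5% |
| 5 | 15 | 0.75 | 21.8% | 5.0% → 6.7% | 10.0% → 13.3% |

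For scale, the exact 95% interval for 1 event in 20 runs from 0.1% to 24.9%, far wider than any shift in the table.

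**Step 4: DSMB blocks.** With m infants exposed in a block and an assumed true harm rate of 10%, the chance of seeing at least one event is 1 − 0.9^m: 41.0% for m = 5, 34.4% for m = 4 and 27.1% for m = 3.

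**Step 5: which second denominator?** Suppose one cord avulses during a failed positioning attempt and the other 19 infants are positioned successfully. All allocated gives 1/20 = 5.0%. Attempted placement also gives 1/20. Successfully positioned gives 0/19, so the event disappears. The added denominator must therefore rest on attempt, not success.

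**The case against.** The strongest defence is that the bail-out rule is part of the intervention as section 6.1 describes it, so the all-allocated set estimates the safety of the strategy and retains harms from aborted attempts. That stands, and it is why the existing table should stay. It does not supply the risk of the procedure once attempted, which a later trial would also need.

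Several stronger readings are tempting but not supported:

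- A reader might infer that every immediately clamped infant was unexposed. Failed positioning is normally discovered by trying, and section 8.4.2 names positioning as the source of cord tension. The draped trolley is also in place before delivery (6.1), so the risk of field contamination is not confined to infants placed on it.
- A reader might carry over the two completed preterm trials in section 1.3.3, where 171 of 179 completed (95.5%, given as 96%) and 8 of 179 (4.5%) did not. Those 8 were clamped early, which does not make them unexposed. The 179 also pool both arms of the larger trial, one of which delayed clamping without planned respiratory support. The figure does not estimate k here.
- A reader might infer that a DSMB boundary is being diluted. The board reviews events and has no stated rate threshold. What remains is that a block may contain fewer attempts than its label suggests.
- A reader might infer that abandoned procedures are hidden. They are not: each counts as a failure in the primary result (5.6, 5.9.2), reasons are recorded (5.3), and SAEs are described individually.

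It is also fair to say that the plan promises frequencies rather than confidence limits; the limits above serve only to show scale.

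**Conclusion.** The point holds as a conditional one. The safety table and the DSMB schedule both count allocations, and section 6.1 lets an allocated infant be clamped before any intact-cord attempt. If that occurs, rates of procedure-specific harm can be understated. If it never occurs, nothing changes. The documents do not support saying that the rates are diluted as a matter of course.

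On the assumption of 1 to 5 unexposed infants in 20, and an event that needs the procedure to occur, the relative understatement is 5% to 25% and the zero-event upper limit rises from 16.8% to between 17.6% and 21.8%. This is modest beside the sampling uncertainty. The case for acting is that safety is a primary aim, the data are largely collected already, and fixing the denominator in advance avoids choosing it after the results are known in an unblinded study of 20.

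**What to change.** Keep the all-allocated safety table unchanged. Add to section 5.9.4 wording such as: *Safety frequencies will also be reported for dyads in whom placing the infant on the trolley with an unclamped cord was attempted, whether or not positioning or intubation succeeded. Exact 95% confidence intervals will be given on both denominators. Infants clamped before any attempt will be listed separately with the reason and their outcomes.*

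State how an attempt is established: the trolley video (5.2.2), the positioning record and the birth-to-clamp time (5.3). The positioning item alone is not enough, because it captures success. Infants whose intubation is not achieved before clamping belong in the attempted set. Field contamination and maternal events should stay on all dyads for whom the trolley was set up.

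In sections 5.11 and 8.4.1, report the number attempted beside the number allocated at each DSMB review. The review schedule need not change, and nothing here touches the clamping rule.

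The cost is one defined variable, one extra column and one extra count per review. The downside is somewhat wider safety limits on the second denominator.

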	
Secondary endpoints: Arterial pH and PaO2 on first blood gas, Oxygenation index [OI] throughout first 24 hours of life [HOL], need for vasopressors (first 24 HOL), presence of severe pulmonary hypertension on first echocardiogram. Need for ECMO during hospitalization, mortality prior to discharge.
 
Tertiary endpoints: Identification of salient themes in parent experiences of the DING intervention, Identification of factors during the intervention that mothers identify as stress inducing or alleviating.

Safety Evaluations	
Safety evaluations will include:
 
Neonatal evaluations: cord avulsion, need for chest compressions during resuscitation, hypothermia on first temperature in the SDU
 
Maternal evaluations: post-partum hemorrhage, need for therapeutic uterotonics, estimated blood loss, contamination of sterile obstetrical field, wound infection

Statistical And Analytic Plan	
Baseline characteristics, the primary, secondary, and tertiary endpoints, and safety evaluations will be summarized by standard descriptive summaries.
 
Secondary outcomes will be compared with historical controls using bivariable analyses

Data and Safety Monitoring Plan	
An independent data and safety monitoring board will review outcomes incrementally after allocation of every 5 subjects to ensure the study does not impose undue extra risk to treated subjects.

---

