## 5.2 Screening and Monitoring Evaluations

### 5.2.1 Medical Record Review – for both interventional arm and historical controls

We will abstract the following variables from the maternal and infant chart:

- Baseline characteristics
    - Prenatal ultrasound findings
    - Gestational age at prenatal diagnosis
    - Date of birth
    - Time of birth
    - Mode of delivery
    - Gestational age
    - Birth weight
    - Sex
    - Race
    - Ethnicity
  - Type and timing of resuscitation interventions in the delivery suite and SDU:
    - Intubation
      - Number of attempts
      - Time of successful intubation
      - Tracheal intubated adverse events, using NEAR4Neos operational definitions
    - Interval between birth and UCC (for interventional arm only)
    - Chest compressions performed
    - Medications and fluids administered
    - Supplemental FiO2
    - Ventilator settings
    - Vital signs during resuscitation (temperature, heart rate, respiratory rate, blood pressure, pulse oximetry)
  - Cardiorespiratory Interventions and diagnostic tests in first 7 days of life
    - Vital signs (heart rate, pulse oximetry, blood pressure)
    - Supplemental FiO2
    - Ventilator settings
    - Vasopressors (type and dose)
    - Laboratory tests (blood gasses, complete blood count, bilirubin level)
    - Echocardiogram findings
  - Clinical outcomes during hospitalization
    - ECMO cannulation (occurrence and day of life)
    - Mortality (occurrence, day of life, and cause)
  - Maternal chart review (outcomes will be ascertained in first 7 days after delivery, or until discharge- whichever period is shorter – for interventional arm only)
    - Estimated blood loss at delivery (all deliveries)
    - Need for therapeutic uterotonics (all deliveries)
    - First post-partum hemoglobin (all deliveries)
-

- OR time (for Cesarean deliveries)
- Contamination of sterile field (for Cesarean deliveries)
- Surgical wound infection (for Cesarean deliveries)

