## **5.4 Safety Evaluation**

Subject safety will be monitored through medical record review and debriefing the clinical staff. We will monitor for the following;

- Neonatal outcomes:
    - Cord avulsion
    - Need for chest compressions during resuscitation
    - Hypothermia (first documented temperature in the SDU <36.0)
  - Maternal outcomes:
    - Any potential contamination of sterile obstetrical field
    - Surgical wound infection
    - Post-partum hemorrhage
    - Estimated blood loss
-

- Need for therapeutic uterotonics
- Any additional concerns from Obstetrical or Neonatal staff

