### **5.7 Secondary Endpoints**

Secondary endpoints include arterial pH and PaO2 on first blood gas, oxygenation index [OI] throughout first 24 hours of life [HOL], need for vasopressors (first 24 HOL), presence of severe pulmonary hypertension on first echocardiogram, need for ECMO and mortality during hospitalization for both the subject allocated to the interventional arm and the historical controls.

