#### Risks From Delayed Cord Clamping (DCC):

DCC after birth is now widely recommended as standard care by multiple professional bodies (Table 1). The safety of this practice for full term newborns and their mothers is well established. The definition of DCC varies significantly across published trials, ranging from 1-5 minutes after birth.

- **Infant Risks:** DCC is associated with an increased risk of hyperbilirubinemia requiring phototherapy. All infants in the DING trial will be monitored for hyperbilirubinemia and treated with phototherapy, according to the American Academy of Pediatrics recommendations. DCC is not associated with increased risk for other studied infant morbidities.
- **Maternal Risk:** DCC is not associated with increased risk of severe post-partum hemorrhage, any post-partum hemorrhage, or other any of the other maternal morbidities that have been studied.

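### Hyperbilirubinemia requiring phototherapy, the infant harm the protocol attributes to delayed clamping, has no assured place in the safety report

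*Combined protocol and SAP*

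**What the plan says.** Section 2.1 makes safety, together with feasibility, the primary objective. On the infant risks of delayed clamping, section 8.4.2 states "DCC is associated with an increased risk of hyperbilirubinemia requiring phototherapy". It adds that no other infant morbidity studied has been linked to the practice. It also promises clinical care: "All infants in the DING trial will be monitored for hyperbilirubinemia and treated with phototherapy".

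The synopsis gives the neonatal safety evaluations as "cord avulsion, need for chest compressions during resuscitation, hypothermia on first temperature in the SDU". Section 5.4 repeats the three items and gives the last a threshold: "Hypothermia (first documented temperature in the SDU <36.0". The secondary endpoints in 5.7 are blood gas values, oxygenation index, vasopressor use, and "presence of severe pulmonary hypertension on first echocardiogram, need for ECMO and mortality during hospitalization".

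Data collection is wider. Section 5.2.1, headed as applying "for both interventional arm and historical controls", includes bilirubin among the laboratory tests of the first 7 days, and 5.2.3 names the first-week peak.

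For analysis, 5.9.4 takes all infants allocated to DING and says: "The frequencies of AEs will be summarized. SAEs (if any) will be described in detail". Section 7.1 first says adverse events are followed for the whole study. It then confines this to the SDU stay and the 24 hours after it, and labels that period the follow-up phase. Sections 3.1.3, 3.3.1 and 4.3 run the follow-up phase to discharge. Sections 5.11 and 8.4.1 have the DSMB review specified safety events after every 5 infants, without listing them.

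**The concern.** The protocol identifies a harm of the practice under test, collects part of the data on it, and then gives it no line in the safety report. Two infant risks that 8.4.2 attributes to the procedure, cord avulsion and cold exposure, both have a line in the safety lists. The one it attributes to delayed clamping itself does not.

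The harm is defined by need for phototherapy, and that is the variable not collected. Peak bilirubin does not replace it: treatment is meant to lower the level, so a treated infant's peak does not show that treatment was needed.

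At stake are the completeness of the safety conclusion, what the DSMB sees, and what a later randomised trial inherits. Section 5.10 says the analytic aim is to supply estimates for designing such trials; a harm that is not tabulated supplies none.

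**Working it through.** The plan states no figure on this point, so there is none to reproduce. The check is mainly of the text.

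**1. Where the infant risks named in 8.4.2 appear**

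| Risk | Safety lists (synopsis, 5.4) | Endpoint (5.6-5.8) | Abstracted (5.2.1, 5.2.3) | Named analysis (5.9) |
|---|---|---|---|---|
| Cord avulsion | yes | no | not by name | yes, as a safety evaluation (5.9.1) |
| Cold exposure | yes | no | temperature | yes, as a safety evaluation (5.9.1) |
| Hyperbilirubinemia requiring phototherapy | no | no | bilirubin yes, phototherapy no | none |

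**2. The adverse event route.** Section 7.3 counts abnormal laboratory findings as possible adverse events, so jaundice could reach the 5.9.4 summary. Whether it does depends on how 7.1 is read.
- Broad reading (whole study, or follow-up to discharge): the first week in hospital is covered.
- Narrow reading (SDU stay plus 24 hours): the bilirubin week is 7 × 24 = 168 hours. The SDU stay is not stated; assume 0 to 24 hours. Coverage is 24/168 = 14.3% to 48/168 = 28.6%, so 85.7% to 71.4% of the week is outside.

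These are shares of hours. The documents give neither time of onset nor a phototherapy rate.

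**3. What the narrow reading could do, over an assumed range.** With true rate p and captured fraction f, the chance of recording at least one case in 20 infants is 1 − (1 − p·f)^20.

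| Assumed p | f = 1/7 | f = 0.25 | f = 0.50 | f = 1 |
|---|---|---|---|---|
| 10% | 25% | 40% | 64% | 87.8% |
| 20% | 44% | 64% | 88% | 98.8% |

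At p = 20%, 20 × 0.20 = 4.0 cases are expected, of which 0.57, 1.0 or 2.0 would be recorded at f = 1/7, 0.25 or 0.50. Both p and f are assumptions.

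**4. What 20 infants can show once the outcome is reported.** Exact (Clopper-Pearson) 95% intervals:
- 0/20: upper limit 1 − 0.025^(1/20) = 16.8%
- 2/20: 1.2% to 31.7%
- 4/20: 5.7% to 43.7%
- 6/20: 11.9% to 54.3%
- 10/20: 27.2% to 72.8%

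Deaths reduce the number who complete the week. Section 1.1 quotes 29% mortality. If all of it fell in week one (a worst case, since the figure is not for the first week), 20 × 0.29 = 5.8 infants would die and about 14 would remain. Then 0/14 leaves 1 − 0.025^(1/14) = 23.2%.

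**5. Control figures.** Section 5.2.1 marks its exceptions, for example "Interval between birth and UCC (for interventional arm only". Bilirubin, chest compressions and resuscitation temperature carry no such mark, so on its wording they are abstracted for controls too. Sections 4.2.2 and 5.9.3 mention only the secondary clinical outcomes for controls. Section 5.9.3 matches each control to a DING infant, so an interval for a difference in proportions depends on the discordant pairs. The documents give no basis for assuming those counts, and none is computed here.

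**The case against.** The strongest reply is that the gap is small. Bilirubin is abstracted for the first week, treatment is promised, the investigator reviews every case, and the synopsis has the DSMB review outcomes, which is broader than specified safety events. Section 5.4 also has an open item for staff concerns. If 7.1 runs to discharge, jaundice judged an adverse event is already counted. This is a 20-infant feasibility pilot.

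Much of that stands. It makes the problem one of reporting, not of care. It does not supply a line in the report: each route depends on someone judging jaundice to be an adverse event or a concern, and none records phototherapy.

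A reader might infer four stronger points that the documents do not support:
- **That the adverse event window would miss most cases.** Only a share of hours can be calculated, and only on the narrow reading. With no onset timing, the share of cases is unknown.
- **That later jaundice definitely falls outside the 5.9.4 summary.** Section 7.1 is ambiguous, so the documents support only that capture is not assured.
- **That a short adverse event window is itself an error.** It may be shorter than follow-up. The problem is that 7.1 also speaks of the whole study and uses a label that other sections define differently.
- **That the plan owes a comparative safety analysis.** Historical controls are planned for the secondary outcomes. Chest compressions and low temperature can occur under immediate clamping, so a DING-only count cannot show extra risk, but setting control figures beside it is a secondary, descriptive improvement.

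**Conclusion.** The point holds as a gap in reporting and should be corrected. A plan with safety in its primary aim names an infant harm of delayed clamping and, followed as written, has no assured route to reporting it. Phototherapy is not collected, and the bilirubin data feed no named analysis. The absence from the lists, endpoints and analyses is a matter of text and rests on no assumption.

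The size of any loss through the adverse event route cannot be fixed. The 71-86% is time outside the narrow window and assumes an SDU stay of 0-24 hours; the recording chances rest on assumed rates and captured fractions. The primary endpoint and sample size are unaffected.

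**What to change.** 1. **Report the named harm.** Add phototherapy in the first week (yes/no) to 5.2.1. List phototherapy and first-week peak bilirubin among the safety evaluations in the synopsis and 5.4, with a stated first-week ascertainment window for these two outcomes. In 5.9.4, report both for all allocated DING infants: number with data, number alive at day 7, a summary of peak bilirubin, and the phototherapy proportion with its exact 95% interval. State that 0/20 leaves an upper limit of 16.8%. Name both among the events the DSMB reviews (5.11, 8.4.1).
2. **Reconcile** the monitoring period and label in 7.1 with 3.1.3, 3.3.1 and 4.3.
3. **Secondary, descriptive only.** Where 5.2.1 already abstracts the item for controls (bilirubin, chest compressions, resuscitation temperature), show the matched-control figures beside the DING figures, without a significance test. Any interval for a difference should respect the individual matching. State that these items do not enter the 5.9.3 requirement for complete control records, so control selection is unchanged. Reconcile 4.2.2 and 5.9.3 with 5.2.1 on what is abstracted for controls.

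Cost: one chart variable in up to 20 DING charts if it is marked for the interventional arm only, a few table rows, and wording changes. Extending phototherapy to controls could mean opening up to 20 more charts and is not needed for the main point. The downside is wide intervals at n = 20 that could falsely reassure, so the report must say that they do not show absence of added risk.
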